5.3 Safety Evaluation

This study presents no more than minimal risk to study participants, as the interventions aim to promote adult smoking cessation, which is universally recommended evidence-based practice. Though adverse events are not anticipated and will not be formally monitored (given the minimal risk nature of the study), should any events be reported to the study team, the information will be immediately shared with the CHOP IRB. We do not anticipate any physical risks to participants. Participants may experience minor psychological discomfort when answering certain questions (e.g., about their smoking habits). In such cases they may choose to not answer these questions.

6 STATISTICAL CONSIDERATIONS

6.1 Primary Endpoint

Parental combusted tobacco quit rate at 1 year, as assessed by validated surveys, biochemically-confirmed at 12-months compared between iEHR + Navigator vs. usual care control.

- Measured by the percentage of parental smokers who have 7-day abstinence (biochemically verified at 12-months).

6.2 Secondary Endpoints

1. To compare parents' self-reported adoption of tobacco free behaviors (quit attempts, use of pharmacotherapy, use of Quitlines and institution of smoking and vaping bans in their homes and cars) between the iEHR + Navigator and usual care arms
2. To establish the incremental cost per quit of the iEHR + Navigator vs. usual care arms
3. To assess the implementation and sustainability of the intervention in the iEHR + Navigator arm (NRT prescription and Quitline referrals as assessed by the parental report around 12-months, the screening survey conducted at check-in, and EHR documentation of screening and services delivery fidelity, before and immediately following implementation, 6, 12, 18, 24, 30, and 36 months).

6.3 Statistical Methods

6.3.1 Baseline Data

The iEHR pre-visit screening questionnaires (Appendix 5 for intervention practices and Appendix 5A for control practices) will collect parental baseline smoking status.

The Parent Enrollment Survey (Appendix 4) will collect additional information about vaping status, stage of readiness to change, demographic information tobacco related attitudes and behaviors, parent's name, and contact information (~ 15 minutes). All parents enrolled will receive a handout from the Research Assistant with food insecurity resources listed.

The primary effectiveness endpoint will be to compare parents' combusted tobacco quit rates between iEHR + Navigator vs. usual care control at 12-months follow-up time. Parents lost to follow-up will be considered as smokers.

The secondary efficacy endpoint will be to compare parents' adoption of tobacco free behaviors between the iEHR + Navigator vs. usual care control arms, to establish the incremental cost per quit of the intervention arm compared to usual care control and to assess the delivery and sustainability of the intervention.

We will also explore outcomes for clinically meaningful subgroups of participants, such as dual users of combustible and e-cigarette tobacco products.

6.3.2 Safety Analysis

This research does not qualify for oversight by the Data Safety and Monitoring Board as defined by NIH guidelines. It is not necessary to establish a board for this study since the interventions aim to promote adult smoking cessation, which is universally recommended evidence-based practice. Though adverse events are not anticipated and will not be formally monitored (given the minimal risk nature of the study), should any events be reported to the study team, the information will be immediately shared with the CHOP and MGH IRBs.

6.4 Sample Size and Power

Sample size calculations are based on having at least 8 practices with a minimum of 5 clinicians per practice. Clinically important and conservative estimates of validated 12-month quit rates based on prior studies are 13.8% in the iEHR + Navigator group and 7% in the usual care control group. These estimates are based on the worst-case scenario from prior studies where all enrolled parents lost to follow-up were assumed to be smokers at 12-month follow-up. The effective sample size needed for the primary outcome accounts for clustering at the clinician and practice level (4 practices per arm x 5 clinicians per practice) with intra-class correlation of .014 calculated from our previous research. By enrolling approximately 100 parents in each practice (400 per arm), we will have 80% power for the primary outcome (iEHR + Navigator vs. usual care control). Effect sizes for outcomes other

than cessation will likely be much greater; the study will have adequate power to detect these differences, shown in our prior studies.

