2.1 Primary Objective

Parental combusted tobacco quit rate at 1 year, as assessed by validated surveys, biochemically-confirmed at 12-months compared between iEHR + Navigator vs. usual care control.

Hypothesis. Parental 7-day combusted tobacco quit rates, as assessed by validated surveys, biochemically-confirmed at 12-months, will be greater for iEHR + Navigator vs. usual care control (outcome for which study is powered).

2.2 Secondary Objectives.

The secondary objectives are to:

[figure not shown]
1. To compare parents' self-reported adoption of tobacco free behaviors (quit attempts, use of pharmacotherapy, use of Quitlines and institution of smoking and vaping bans in their homes and cars) between the iEHR + Navigator & usual care arms
2. To establish the incremental cost per quit of the iEHR + Navigator vs. usual care arms
3. To assess the implementation and sustainability of the intervention in the iEHR + Navigator arm (NRT prescription and Quitline referrals as assessed by the parental report around 12-months, the screening survey conducted at check-in, and EHR

documentation of screening and services delivery fidelity, before and immediately following implementation, 6, 12, 18, 24, 30, and 36 months).

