3.3.2 Total Number of Study Sites/Total Number of Subjects Projected

The study will be conducted at a minimum of 8 primary care sites at CHOP with approximately 40 clinicians participating across these 8 sites, and proportionally more clinicians if other sites are added.

Our goal is to stop recruitment when 400 parent subjects are enrolled per arm in the longitudinal cohort (800 across both arms). The study has been designed to achieve this goal by recruiting 100 parents from each of four sites per arm, and for this situation we will have 80% power for the primary outcome (iEHR + Navigator vs. usual care control), for a clinically meaningful difference in smoking cessation rates. If some practices accrue subjects at a rate which makes it unlikely that these practices can achieve the recruitment goal of 100 subjects, then we will estimate the likely shortfall, and increase the recruitment goals in faster-accruing practices in order to attempt to preserve statistical power. We may also add additional practices to maximize the likelihood of meeting the recruitment goal of at least 400 parents enrolled in each arm. If we add practices, we will do so in pairs, matched by practice size and Medicaid rate, and randomly assigned to the control and intervention groups. If the study must be terminated before the recruitment goal, this termination will be made exclusively for reasons (such as time and budget) which are unrelated to study outcomes.

In the intervention practices, a minimum of one clinician and one key staff will complete an in-depth qualitative interviews 6-weeks following implementation and after 12, and 24 months.

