9 STUDY ADMINISTRATION

9.1 Treatment Assignment Methods

9.1.1 Randomization

In this 2-arm cluster randomization of practices to 'iEHR +Navigator' and 'usual care control' arms, we will recruit at least four matched pairs of practices through the CHOP network. Practices will be matched with respect to size and Medicaid rate. Within each of these pairs of practices, we will assign one to the intervention and the other to control, using computer generated random allocation. When the four assignments are complete, a fifth computer-generated random number will assign either "A" or "B" to the intervention. The statisticians will be blinded as to which of "A" and "B" is the intervention until the analyses are completed. In the event that a practice drops out, we will replace it with the most similar practice based on practice size and Medicaid rate from the pool of unassigned and interested practices. In the event the enrollment is slower than projected, we will add additional practices from the CHOP network, with practices matched in pairs based on practice size and Medicaid rate, from the pool of unassigned and interested practices. We will randomly allocate these practices in pairs to the control and intervention arms, as needed and in decreasing order of projected enrollment rate.

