In our intention-to-treat analysis, all participants lost to follow-up will be considered smokers. We will also use multiple imputation techniques, as appropriate to impute missing data. We will use generalized linear mixed-effects models (Gaussian, logistic, or Poisson, as appropriate) to compare the primary outcome between arms. To the extent allowed by the sample, we will build a logistic regression model that includes potential confounding factors, particularly those that are unbalanced between iEHR+Navigator vs usual care control groups to compare the parental 7-day quit rates. We will attempt to identify predictors of parental quitting to determine whether any of these factors modify intervention effect. To determine whether the intervention effect differs among subgroups, we will test the interaction between intervention group and these predictors. Specifically, to the extent allowed by our sample size, exploratory analyses will compare quit rates in subgroups of smokers characterized by cigarettes per day, e-cigarette use, number of smokers in the home, demographic variables (parent sex, age, race, education, child age) and treatment use. We will conduct a difference in difference analyses from baseline to follow up to evaluate the effect of the intervention on changes in smoking related factors like mean cigarettes per day and daily smoking rates.

Secondary outcomes

1. Rates of smokefree homes and cars, use of NRT and duration of use, and quitline enrollment, as assessed by validated surveys of parents, will be compared between iEHR+Navigator and usual care control arms. Change in parental smoking inside homes and cars, use of NRT, and receiving services from cessation programs will be based on the baseline and 12-months enrollment visit, comparing change from baseline to 12 months between intervention groups and usual care control practices. We will follow a similar analysis strategy to that stated above in primary outcome analysis.

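### The stated 80% power fits a calculation with no practice-level correlation, although practices are randomised; if the ICC of .014 is a practice-level value, power is about 54% (two-sided .05 assumed)

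*Protocol*

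**What the plan says.** Protocol 6.4 sets out the calculation for the primary outcome, biochemically confirmed 7-day abstinence at 12 months. The assumed rates are "13.8% in the iEHR + Navigator group and 7% in the usual care control group". The section says that the effective sample size "accounts for clustering at the clinician and practice level (4 practices per arm x 5 clinicians per practice) with intra-class correlation of .014", and concludes: "By enrolling approximately 100 parents in each practice (400 per arm), we will have 80% power for the primary outcome".

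Section 3.3.2 repeats the figure and ties it to 100 parents from each of four sites per arm: "for this situation we will have 80% power for the primary outcome".

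Sections 3.2 and 9.1.1 make the practice the randomised unit, in matched pairs: "Within each of these pairs of practices, we will assign one to the intervention and the other to control".

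Section 2.1 words the hypothesis directionally: quit rates "will be greater for iEHR + Navigator vs. usual care control (outcome for which study is powered").

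The SAP contains no power calculation. For the analysis it says: "We will use generalized linear mixed-effects models (Gaussian, logistic, or Poisson, as appropriate) to compare the primary outcome between arms". It names no random-effect level and no degrees of freedom. Neither document gives alpha, sidedness, a design effect, or a second ICC.

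**The concern.** When practices are randomised, correlation between parents of the same practice inflates the variance of the arm comparison, whichever clinician they see. With about 100 parents per practice, even a small practice ICC matters. Section 6.4 says that practice-level clustering has been allowed for, but the planned 400 per arm and the printed 80% both agree with a calculation that allows for clinician clusters only.

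This is the outcome on which the trial's size rests. If true power is nearer 54% than 80%, a null result could easily be misread as evidence of no effect. The recruitment contingency is also affected. Sections 3.3.2 and 4.1 would raise targets in faster-accruing practices to protect power, but larger clusters cannot fully replace lost practices when the practice ICC is not negligible.

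**Working it through.** **Inputs.** From Protocol 6.4: rates .138 and .07; 400 parents per arm; 4 practices per arm, 5 clinicians per practice, hence 100 parents per practice and 400/20 = 20 per clinician; ICC .014. Assumed, because not stated: two-sided alpha .05. No dropout inflation is needed, since the assumed rates already count losses as smokers.

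**Formulas.** A parent shares a clinician with 19 others, and shares the practice but not the clinician with 80 others. With within-clinician correlation .014 and practice correlation ρ:

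- Design effect: DE = 1 + 19 × .014 + 80ρ
- Effective sample per arm: n = 400/DE
- SE = √[(.138 × .862 + .07 × .93)/n] = √(.184056/n)
- Power = Φ(.068/SE − 1.96)

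Setting ρ = .014 gives 1 + 99 × .014, the usual formula for practice clusters of 100.

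**Step 1: reproduce the plan's figure.** With ρ = 0, DE = 1.266 and n = 400/1.266 = 316. SE = .02414, .068/.02414 = 2.817, and power = Φ(.857) = 80.4% (80.1% with pooled variance). In reverse, the pooled formula needs 316 per arm for 80%, and 316 × 1.266 = 400. Ignoring clustering altogether gives 88.7% (pooled 88.5%). So two-sided .05 with clinician clusters alone reproduces both the planned number and the stated power.

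**Step 2: the practice as cluster, ICC .014.** DE = 1 + 99 × .014 = 2.386 and n = 400/2.386 = 168. SE = .03313, .068/.03313 = 2.052, and power = Φ(.092) = 53.7% (pooled 53.2%).

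**Step 3: values in between.** Within-clinician correlation .014, two-sided .05; the values of ρ are illustrative:

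| Practice ICC ρ | DE | Effective n per arm | Power | Intervention rate detectable at 80% power (against 7%) |
|---|---|---|---|---|
| 0 | 1.266 | 316 | 80.4% | 13.8% |
| .002 | 1.426 | 281 | 75.6% | 14.2% |
| .004 | 1.586 | 252 | 71.1% | 14.7% |
| .007 | 1.826 | 219 | 65.0% | 15.4% |
| .014 | 2.386 | 168 | 53.7% | 16.8% |

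The last row is a difference of 16.8 − 7 = 9.8 points, against 13.8 − 7 = 6.8 assumed.

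**Step 4: the largest practice ICC that leaves 80%.** Two-sided, 80% needs an effective n of 312.4, so DE may be at most 400/312.4 = 1.280 and ρ at most (1.280 − 1.266)/80 = .0002.

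**Step 5: one-sided .05.** The effective n needed is 246.1, so DE may be at most 400/246.1 = 1.625 and ρ at most (1.625 − 1.266)/80 = .0045. Power is 88.0% at DE 1.266 and 65.8% at DE 2.386.

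**Step 6: small-sample sensitivity.** The figures above treat the variance as known. An unmatched comparison of eight practice means on a t distribution with 6 degrees of freedom gives 65%, 60%, 56%, 50% and 41% for the five rows. A nested simulation (20,000 runs, 8 practices × 5 clinicians × 20 parents) agrees: 66%, 61%, 56%, 51% and 42%, and with known variance 81%, 75%, 70%, 66% and 55%.

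**The case against.** The 80% is reproducible from the protocol's own inputs, so what is shown is an undisclosed basis, not a proven error. The ICC comes from the team's earlier research, which cannot be seen here. If it is a within-clinician value, the practice ICC can be anything up to .014, and 54% is the boundary case; at half that value power is 65%. Alpha is an assumption, the hypothesis is directional, and one-sided .05 would support 80% up to a practice ICC of .0045. Matching on size and Medicaid rate, and the covariate-adjusted model in the SAP, may remove some between-practice variance. Eight practices is a minimum: with 400 per arm and practice ICC .014, six practices per arm would give about 63% and eight about 68%. The 6-df figures describe a test that the plan does not name.

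Much of this stands as a limit on what can be concluded. The level of the ICC is unknown, and 54% is conditional on it. The t-based figures are a sensitivity only. None of it restores the 80%, however. Section 6.4 says practice-level clustering is included, and the best-fitting reconstruction leaves no room for it. One-sided testing gives 66% at .014, and 88%, not 80%, at the design effect that fits the planned 400. Section 6.4 claims no gain from matching, and the documents do not allow one to be computed; a matched analysis of four pairs would have 3 degrees of freedom. Added practices are beside the point, because 3.3.2 ties the 80% to four sites of 100 per arm.

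**Conclusion.** The concern holds. As printed, the 80% sits at the most favourable end of what the protocol's ICC allows: two-sided power runs from about 80% with no practice-level correlation to about 54% (53.2% pooled, 53.7% unpooled) if the practice ICC is .014. This rests on two-sided alpha .05, equal clusters, a normal approximation and no gain from matching. The clinician-only design effect is the most plausible reconstruction, not the only possible one; one-sided .05 with an unprinted practice ICC of about .0045 would also give 80%. A reader cannot tell which applies. Because the practice is the randomised unit and the protocol names this as its powered outcome, the figure must be corrected or its basis documented.

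**What to change.** In Protocol 6.4 and 3.3.2, compute power with the practice as the randomised cluster. State alpha and sidedness, the level and source of the .014, any second ICC, and the design effect.

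- **If .014 is the practice-level ICC**, the text could read: *With 4 practices of about 100 parents per arm, a practice-level ICC of .014 (design effect 2.386, effective n about 168 per arm) and two-sided alpha .05, power for 13.8% vs 7% is about 54%; the intervention rate detectable with 80% power against 7% is 16.8%.*
- **If .014 is a within-clinician ICC**, give the practice-level ICC with its source and recompute, or print the 54–80% range by practice ICC. The 80% can stay only if a near-zero practice ICC is documented, or if one-sided .05 is declared together with a practice ICC of no more than about .0045.

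An added line, labelled as sensitivity, could give the result on 6 degrees of freedom with matching ignored (41% to 65%), since the SAP's mixed model does not say how it handles so few clusters.

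The cost is wording and a recalculated figure in two sections, probably less favourable than the present one. Correcting the statement needs no extra participants, visits or data.

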7 STUDY INTERVENTION

7.1 Description

The iEHR part of the intervention arm consists of an innovative electronic platform for screening and automated support of the smoking cessation workflow to parents who smoke. iEHR will include automated EHR-generated NRT prescription/referral to BrightMedical, automated enrollment in the free Quitline and SmokefreeTXT program, and a brief motivational message delivered by the clinician (as prompted by the EHR).

Additional support of CHNs will be offered to all parents in the intervention arm. These CHNs will work with offices to provide customized smoking cessation support to household tobacco users through phone follow-up, ensuring access to medications and services, and/or home visits, depending on the needs of each family and as study resources allow. See a detailed description of the intervention and its components under *section 4.2.1*.

7.1.1 Treatment Compliance and Adherence

N/A

8 SAFETY MANAGEMENT

8.1 Clinical Adverse Events

Clinical adverse events (AEs) will be monitored throughout the study. This is described in 9.4.2.

8.2 Adverse Event Reporting

Since the study procedures are not greater than minimal risk, serious AEs (SAEs) are not expected. If any unanticipated problems related to the research involving risks to subjects or others happen during the course of this study (including SAEs) they will be reported to the IRB in accordance with CHOP IRB SOP 408: Unanticipated Problems Involving Risks to Subjects. AEs that do not meet prompt reporting requirements will be tracked and documented internally by the study team but not submitted to the IRB (as continuing reviews are not required). This is described in 9.4.2.

9 STUDY ADMINISTRATION

9.1 Treatment Assignment Methods

9.1.1 Randomization

In this 2-arm cluster randomization of practices to 'iEHR +Navigator' and 'usual care control' arms, we will recruit at least four matched pairs of practices through the CHOP network. Practices will be matched with respect to size and Medicaid rate. Within each of these pairs of practices, we will assign one to the intervention and the other to control, using computer generated random allocation. When the four assignments are complete, a fifth computer-generated random number will assign either "A" or "B" to the intervention. The statisticians will be blinded as to which of "A" and "B" is the intervention until the analyses are completed. In the event that a practice drops out, we will replace it with the most similar practice based on practice size and Medicaid rate from the pool of unassigned and interested practices. In the event the enrollment is slower than projected, we will add additional practices from the CHOP network, with practices matched in pairs based on practice size and Medicaid rate, from the pool of unassigned and interested practices. We will randomly allocate these practices in pairs to the control and intervention arms, as needed and in decreasing order of projected enrollment rate.

9.1.2 Blinding

The practices in each pair (the four initial pairs, and any subsequent pairs added in the event of slow accrual) will be randomly assigned labels "A" and "B". The intervention will be blinded in a separate randomization with either the label "A" or the label "B", and the other label will be assigned to the control practice. The statisticians will be blinded as to which of "A" and "B" is the intervention until the analyses are completed.

9.1.3 Unblinding

After the analyses are completed, the arms will be unblinded.

[figure not shown]
9.2 Data Collection and Management

The plan will be consistent with CHOP Policy A-3-6: Acceptable Use of Technology Resources that defines the requirements for encryption and security of computer systems. Only investigators and trained staff will have access to study information, both raw data and machine-readable files. The final dataset that will be used for the analyses will be HIPPA-limited (e.g., containing birth dates, dates of service, zip codes). Identifiable patient health information collected will also be managed in accordance with 42 CFR Parts 160 and 164 (HIPAA) federal regulations pertaining to the privacy of patient-related health information. All investigators and research staff will be HIPAA and human subjects research certified through the completion of web-based human subjects protection training, such as the CITI course. Additionally, the computer systems at the MGH and CHOP containing confidential data will have a level and scope of security that equals or exceeds those established by the Office of Management and Budget (OMB) in OMB Circular No. A-130 - Security of Federal Automated Information Systems.

